## D. Missing Data

### 1. Missing Dates

Unless stated otherwise as below, missing dates will not be replaced with imputed values. The sections below will address how missing dates will be handled for the analyses.

#### **Missing or Partial Adverse Events, Medications and Procedure start or stop date:**

For partial start dates:

- If the year is unknown, no imputation will be performed, and the event will be

- assumed as treatment-emergent or concomitant.
- If the year is known and the month and day are unknown, then:
    - If the year matches the year of the first dose date, then impute the month and the day the same as first dose date.
    - If the year is not the same year of the first dose, then month and day will be imputed as 01 January.
  - If the month and year are known and the day is unknown, then:
    - If the month and year match the month and year of the first dose date, then impute the day the same as first dose date.
    - If year and month are not the same as the first dose date, then the day will be imputed as "01".

For partial end-dates:

- If the year is missing, no imputation will be performed, and the event will be assumed as ongoing.
- If the year is present and both month and day are missing and the year is not the same as the last study date (including date of last visit or lost to follow-up date if early terminated), then the month and day will be imputed as the last day of the year, 31 December.
- If the year is present and both month and day are missing and the year is the same as the last study date (including date of last visit or lost to follow-up date if early terminated), then the month and day will be imputed as the last study date.
- If the year and month are present and only the day is missing, and the year and month is not the same as the last study day (including date of last visit or lost to follow-up date if early terminated) then the day will be imputed as the last day of the month.
- If the year and month are present and only the day is missing, and the year and month is the same as the last study day (including date of last visit or lost to follow-up date if early terminated) then the day will be imputed as the last day of the study.

If the imputed end date is before the corresponding start date, then the end date will be set to the start date.

If a subject died during the study and date of death is missing, then it will be set to the end of study date.

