6.6.4 Rescue Medications

Subjects who require topical corticosteroids, calcineurin inhibitors, or PDE4 inhibitor medications that could directly impact AD disease activity prior to Day 57 will be withdrawn from study drug and the study if requiring such topical therapies prior to Day 57.

Starting at Day 57, rescue medications for persistent, intolerable AD activity may be considered by the Investigator. Investigators must document evidence of continued active AD with EASI unchanged from or greater than the Baseline EASI score over 2 consecutive visits before initiating therapy. All subjects requiring rescue therapy between Day 57 (Week 8) and Day 113 (Week 16) will remain in the study and on study drug until Week 16.

After the end of treatment at Day 113 and during the follow-up phase, subjects may also initiate rescue if either the subject or investigator feels that there is persistent, intolerable AD activity.

Permitted rescue medications include low- to moderate-potency (class IV-class VII) topical corticosteroids ([Appendix 14](#)) and should be applied only to problem areas. A topical calcineurin inhibitor, topical PDE4 inhibitor (e.g., crisaborole), or low-potency topical steroid may be used on the face if affected. Subjects who require rescue therapy will be considered non-responders for all efficacy endpoints with data imputed for subsequent continuous endpoints for all time points as detailed in the Statistical Analysis Plan (SAP). Ideally, the specified medication for rescue treatment would be supplied by the clinic so that the tube could be weighed prior to administration. In addition, use of the specified medication should be recorded in the e-Diary, and the medication should be brought to clinic at subsequent visits to assess amount of medication used.

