### A. Estimand

The main estimands associated with the primary and key secondary endpoints to support regulatory decisions are described in the following table:

Attribute	Description
Treatment	RPT 193-02 (50mg, 200mg, 400mg) and Placebo
Population	Adult subjects with moderate-to-severe AD as defined by the inclusion/exclusion criteria
Endpoint	
Primary Endpoint
 
 
% change in Eczema Area Severity Index (EASI) from baseline at Week 16
 
 
Key Secondary Endpoints
 
 
% of subjects achieving a Validated Investigator Global Assessment (vIGA) score of 0 or 1 at Week 16
 
% of subjects achieving EASI-75, defined as a 75% reduction in EASI from baseline to Week 16
 
% change from baseline in PP-NRS from an itch daily e-Diary at Week 16.
 

Intercurrent Events	
 
Early termination of study treatment: Subjects who discontinue from the study treatment prior to Week 16 will be analyzed by the treatment policy strategy, i.e., all data collected after termination of study treatment but prior to rescue medication will be included in the analysis. Missing post discontinuation values will be imputed according to details provided below.
 
Use of rescue medications: Subjects who use rescue medication during the 16-week treatment period will be analyzed by the hypothetical strategy. All EASI/vIGA/PP-NRS scores collected after the start of rescue medication will be set to missing. The missing data after the use of rescue medication will be imputed to follow a similar profile as the placebo group.
 

Population-level Summary	
Primary Endpoint
 
 
Difference in mean percent change from baseline in EASI score between each RPT193 dose and placebo at Week 16.
 
 
Key Secondary Endpoints
 
 
Difference in percentage of subject achieving vIGA of 0 or 1 between each RPT193 dose and placebo at Week 16.
 
Difference in percentage of subject achieving EASI-75 between each RPT193 dose and placebo at Week 16.
 
Difference in mean percent change from baseline in PP-NRS
 

	between each RPT193 dose and placebo at Week 16.
--	--

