## 2. Missing EASI, vIGA and PP-NRS

Missing data will be imputed for the primary and secondary endpoints, which includes the composite EASI score, vIGA and PP-NRS for the 16-week treatment period. Assessment after the use of rescue will be set to missing prior to any imputation. No imputation is planned for the follow-up period. The following missing data techniques will be utilized:

**Last Observation Carried Forward (LOCF):** All missing data up to Week 16 will be imputed by the last observed value carried forward for any subsequent missing values. For patients with only baseline value, the baseline value will be carried forward to Week 16. This will be applied to the continuous endpoints of composite EASI score and PP-NRS.

**Worst Observation Carried Forward (WOCF):** All missing data up to Week 16 will be imputed by the worst observed value carried forward for any subsequent missing values. For patients with only baseline value, the baseline value will be carried forward to Week 16. This will be applied to the continuous endpoints of composite EASI score and PP-

NRS.

**Treatment Failures (TF):** All missing binary endpoint data up to Week 16 will be imputed as failure. This will be applied to key secondary binary endpoints of EASI-75, responder and vIGA score of 1 or 0, and other secondary endpoints of EASI-50, EASI-90, at least 2-point reduction in vIGA, at least 3-point/4-point reduction PP-NRS.

**Observed Cases (OC):** No missing data will be imputed. All observed data will be included. To reiterate, data after the rescue medication will be set to missing.

**Multiple Imputation (MI) under MAR:** Missing continuous endpoints of EASI, and PP-NRS will be imputed using the multiple imputation (MI) with analysis of covariance (ANCOVA) model as the primary analysis for time-points at which no value is observed. MI will be performed under missing at random (MAR) assumption. The MI is a simulation-based approach where missing values are replaced by multiple Bayesian draws from the conditional distribution of missing data given the observed data and covariates, creating multiple completed data sets.

For the EASI assessment, all missing scheduled visits as outlined in the protocol will be imputed. For the PP-NRS assessment, all missing weekly visits will be imputed.

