## **G. Prior and Concomitant Medications**

Prior medications are defined as any medication that stopped before the date of the first dose of study drug. These medications will be recorded on both the "Prior Dupilumab and/or Tralokinumab Meds" and the "Prior and Concomitant Medications" eCRF form. Concomitant medications are defined as any medication that was ongoing or ended at the date of first dose, or any medication that started on or after the date of first dose. These medications will be recorded on the "Prior and Concomitant Medications" eCRF form.

All medications will be coded using the World Health Organization Drug Dictionary (WHO-DD) version B3 Global September 2021. Prior and concomitant medications will be summarized separately by Anatomical-Therapeutic-Chemical (ATC) level 4 classification and PT by treatment group and overall.

Medications that are indicated as rescue medications will also be summarized. Detailed information of rescue medications/procedures including duration of use and incidence of use will be summarized by topical and systemic groups. Kaplan-Meier (K-M) curves for time to first rescue use will be generated. The duration of use will be calculated based on the first start date and end date by topical and systemic groups. Missing dates will be imputed following Section IV.D.

All medications will be presented in a listing. A separate listing will be presented to include the rescue medications.

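### The SAP's partial start-date rule has no bound for rescue medication and can delete valid pre-rescue scores, including an observed Week 16 EASI when rescue began in follow-up

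*SAP*

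**What the plan says.** SAP IV.D.1 has a single set of start-date rules under the heading "Missing or Partial Adverse Events, Medications and Procedure start or stop date". Rescue is not exempted. The branches that matter for rescue are:

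- Year known, month and day unknown, same year as first dose: "If the year matches the year of the first dose date, then impute the month and the day the same as first dose date".
- Year known, month and day unknown, different year: "If the year is not the same year of the first dose, then month and day will be imputed as 01 January".
- Month and year known, day unknown, month different from that of first dose: the first of the month.

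IV.D.1 also says that missing dates are not otherwise replaced. SAP VII.G, in the paragraph on rescue summaries and time to first rescue, adds "Missing dates will be imputed following Section IV.D".

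The rescue start date also drives the efficacy analysis. SAP II.A says "All EASI/vIGA/PP-NRS scores collected after the start of rescue medication will be set to missing", and SAP IV.D.2 fixes the order: "Assessment after the use of rescue will be set to missing prior to any imputation". SAP VI.D.2 censors the time-to-response endpoints at the last assessment before rescue.

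Protocol 6.6.4 allows rescue from Day 57 and again in follow-up after Day 113. For rescue on treatment, "Investigators must document evidence of continued active AD with EASI unchanged from or greater than the Baseline EASI score over 2 consecutive visits" is required first. Follow-up rescue carries no EASI condition.

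**The concern.** Each imputing branch picks an early date, and none is bounded by a visit at which no rescue was reported. For adverse events an early date leans towards calling the event treatment-emergent. For masking efficacy data, an early date discards valid observations.

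Two kinds of information are at stake. If rescue truly began in follow-up, the Week 16 value is a valid observation under the estimand, yet an early imputed start can remove it and treat the subject as rescued on treatment. If only the year is known, the imputed start can be the first dose itself. The subject then keeps baseline only, and the control-based imputation supplies a placebo course where the record may show non-response.

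**Working it through.** **The plan's own figure.** The documents give no figure on partial rescue dates. The only design number used below is the arm size: 60/(1 − 0.10) = 66.7, rounded up to 67, as in SAP III.C.

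**Two dated examples (first dose 16 Jan 2023 = Day 1, visits on schedule).**

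- Rescue on 25 May 2023 is Day 130. With the day missing, the imputed start is 1 May, Day 106. The Week 16 EASI and vIGA at Day 113 (8 May) fall after it and are blanked. The Week 16 PP-NRS window, Days 107 to 113 in SAP IV.C, also falls wholly after it.
- Rescue on 15 April 2023 is Day 90. With only the year known, the imputed start is Day 1, and Weeks 2, 4, 8 and 12 are blanked.

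**All dates.** The IV.D.1 rule was applied to every first-dose date in one 365-day year and every true rescue day. A visit (Days 15, 29, 57, 85, 113) counts as wrongly lost if it falls after the imputed start but on or before the true start. Assumptions: first-dose dates and rescue days evenly spread, visits on schedule.

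| True rescue start | Known part | Mean shift (days) | At least one valid EASI lost | Mean visits lost | All post-baseline pre-rescue EASI lost | Week 16 EASI lost |
|---|---|---|---|---|---|---|
| Days 57–112 | month, year | 14.7 | 52% | 0.53 | 0% | masked anyway |
| Days 57–112 | year | 73.5 | 96% | 3.05 | 81% | masked anyway |
| Days 114–169 | month, year | 14.7 | 25% | 0.25 | 0% | 25% |
| Days 114–169 | year | 112.9 | 92% | 3.87 | 65% | 92% |

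The imputed start was never later than the true one. For year-only dates with rescue on Days 57–112, it was the first dose in 77% of cases and before Day 57, the earliest permitted rescue, in 92%.

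**Day missing, rescue on treatment.** Suppose the shift is 0 to 29 days and rescue starts 0 to 6 days after the later qualifying visit (the lag is assumed). That gives 30 × 7 = 210 combinations.

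- Later qualifying visit on or after the imputed start: the sum of (30 − u) for u = 0 to 6 is 189, and 189/210 = 90%. Counting only visits strictly after the start gives 182/210 = 87%.
- Earlier qualifying visit, 28 days before: this needs shift ≥ u + 28, which holds in 3 combinations (28 with u = 0; 29 with u = 0 or 1). 3/210 = 1.4%.

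One EASI at or above baseline therefore nearly always survives. It stays a predictor, because the Appendix II code regresses Week 16 on Weeks 2 to 12.

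**Size when all post-baseline scores go (rescue on treatment).** Let m be the placebo mean percent change and r the correlation between pre-rescue and Week 16 change, on a common scale. With a pre-rescue change of 0% kept, the predicted Week 16 change is m + r(0 − m). With it deleted, the prediction is m. The difference is r × |m| towards improvement. Neither m nor r is in the documents. Over assumed ranges:

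- m = −25, r = 0.5: 12.5 points for the subject; 12.5/67 = 0.19 on the arm mean.
- m = −45, r = 0.8: 36 points for the subject; 36/67 = 0.54 on the arm mean.

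**The case against.** A reader might infer that the rule routinely deletes the visit that triggered rescue and turns documented failures into average placebo courses. For the day-missing case the documents do not support that. Protocol 6.6.4 requires two consecutive visits, and the earlier one almost always survives. The 90% rests on an assumed lag of 0 to 6 days; with rescue days spread evenly, any loss at all occurs in 52%. When rescue truly began before Week 16, the Week 16 score is masked whatever the imputed date, so only predictors are lost.

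The link to masking is also an inference. The VII.G sentence sits among the rescue summaries, and neither II.A nor IV.D.2 says that masking uses an imputed date. The link follows from the scope of IV.D.1 and the absence of another rule. That stands as a caveat, and it is also a reason to state the rule.

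Partial dates should be uncommon: on-treatment rescue needs prior documentation, use is entered in the e-Diary, and rescue is reviewed at visits from Day 57. This stands. However, the SAP does not say that the e-Diary overrides a partial eCRF date.

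Finally, LOCF and WOCF carry baseline forward for a subject left with baseline only, and TF counts that subject as a failure. A discrepancy between analyses could show. It would not identify the cause, because these analyses start from the same masked data.

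**Conclusion.** The gap is real and minor. As written, a partial rescue start can be placed before visits at which the subject had not been rescued, and valid scores are then dropped from the primary, key secondary and time-to-response analyses. The consequential cases are follow-up rescue, where an observed Week 16 value can go, and year-only dates in the first-dose year, where all post-baseline scores go. For rescue before Week 16 with only the day missing, the effect is small.

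A reader might infer that the results would look better for RPT193. The documents do not support that. Where rescue on treatment loses all its scores, the imputed value moves towards a placebo course in whichever arm the subject belongs to, placebo included. For follow-up rescue there is no EASI condition, so the direction is not fixed. Nor does the SAP state that the rule was meant to be conservative for adverse events; that is only a plausible reading.

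The calendar percentages rest on evenly spread dates, and the per-subject shift on assumed placebo change and correlation. The frequency of partial rescue dates is not given and is probably low.

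**What to change.** Exempt rescue medication from the IV.D.1 start-date rule for masking and censoring, and state in IV.D.2 which date is used:

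1. If the e-Diary gives a complete first-use date consistent with the known parts, use it.
2. Otherwise use the earliest date consistent with the known parts that falls after the last visit review, before the first recorded rescue use, at which no rescue was reported.
3. Do not treat a missing e-Diary entry as evidence of no use. Protocol 6.4 anticipates subjects missing more than 20% of entries.

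The limit in step 2 to reviews before first recorded use is needed. With intermittent use, a later visit without rescue could otherwise push the start too late and keep scores affected by rescue.

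In the examples, suppose no e-Diary date exists and the Week 18 review (Day 127) and Week 12 review (Day 85) respectively reported no rescue. The starts become Day 128 and Day 86, and no scheduled pre-rescue EASI is lost.

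The cost is a few SAP lines and slightly more programming; the e-Diary and visit-review data are already collected. There is a small risk of keeping a score if rescue use went unreported at a visit. SAP I.B allows changes until treatment unblinding, so this should be settled before the Week 16 efficacy analysis in SAP IV.F.

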## 2. Missing EASI, vIGA and PP-NRS

Missing data will be imputed for the primary and secondary endpoints, which includes the composite EASI score, vIGA and PP-NRS for the 16-week treatment period. Assessment after the use of rescue will be set to missing prior to any imputation. No imputation is planned for the follow-up period. The following missing data techniques will be utilized:

**Last Observation Carried Forward (LOCF):** All missing data up to Week 16 will be imputed by the last observed value carried forward for any subsequent missing values. For patients with only baseline value, the baseline value will be carried forward to Week 16. This will be applied to the continuous endpoints of composite EASI score and PP-NRS.

**Worst Observation Carried Forward (WOCF):** All missing data up to Week 16 will be imputed by the worst observed value carried forward for any subsequent missing values. For patients with only baseline value, the baseline value will be carried forward to Week 16. This will be applied to the continuous endpoints of composite EASI score and PP-

NRS.

**Treatment Failures (TF):** All missing binary endpoint data up to Week 16 will be imputed as failure. This will be applied to key secondary binary endpoints of EASI-75, responder and vIGA score of 1 or 0, and other secondary endpoints of EASI-50, EASI-90, at least 2-point reduction in vIGA, at least 3-point/4-point reduction PP-NRS.

**Observed Cases (OC):** No missing data will be imputed. All observed data will be included. To reiterate, data after the rescue medication will be set to missing.

**Multiple Imputation (MI) under MAR:** Missing continuous endpoints of EASI, and PP-NRS will be imputed using the multiple imputation (MI) with analysis of covariance (ANCOVA) model as the primary analysis for time-points at which no value is observed. MI will be performed under missing at random (MAR) assumption. The MI is a simulation-based approach where missing values are replaced by multiple Bayesian draws from the conditional distribution of missing data given the observed data and covariates, creating multiple completed data sets.

For the EASI assessment, all missing scheduled visits as outlined in the protocol will be imputed. For the PP-NRS assessment, all missing weekly visits will be imputed.

The missing EASI, and PP-NRS values will be imputed 100 times to generate 100 complete data sets by using the Markov Chain Monte Carlo (MCMC) method implemented with the SAS PROC MI procedure. The example code can be found in Appendix II.

100 imputed datasets will be generated following the 2 steps below:

1. The monotone missing pattern is induced by Markov Chain Monte Carlo (MCMC) method in MI procedure. The monotone missing pattern means that if a subject has missing value for a variable at a visit, then the values at all subsequent visits for the same variable are all missing for the subject.
2. The missing data at subsequent visits will be imputed using the regression method for the monotone pattern with adjustment for covariates including treatment groups, the randomization stratification factors of baseline vIGA score (3,4), and prior dupilumab or tralokinumab use (yes or no), and relevant baseline value.

These completed datasets are then analyzed using standard analysis methods and results combined (averaged) to present one MI result.

#### **Control-based PMM-MI procedures for EASI, PP-NRS, and vIGA under MNAR**

Similar to MI under MAR, but for EASI, PP-NRS, and vIGA, data collected after the intercurrent events of rescue medication or treatment discontinuation in the RPT193 arm will be assumed missing not at random (MNAR) and resemble missing data from subjects from the placebo arm who do not discontinue treatment permanently/receive rescue medication. Imputation of missing data at Week 16 will be done using a control-based Pattern Mixture Model Multiple Imputation (PMM-IM) where missing data in the study drug (RPT-193) arm as well as the placebo arm will be imputed from observed data in the placebo arm.

The intermittent missing data will be imputed separately for each treatment group using the Markov Chain Monte Carlo (MCMC) method implemented with the SAS PROC MI procedure. 100 imputed datasets will be generated.

For each of the 100 datasets a monotone missing data pattern will be achieved. The monotone missing values will then be imputed from subjects in the placebo group using the SAS PROC MI procedure with MNAR statement. This assumes that the missing data will follow a similar profile as the placebo group.

After the completion of the imputation, the assessments collected after the discontinuation of study treatment yet before to the use of rescue medication will be restored. The example code can be found in Appendix II.

The categorical secondary endpoints will be derived from the imputed scores in each MI datasets.

